Responsibilities include: study planning, organization of steering committee meetings, provides annual risk report to the Human Research Protection Office at Washington University, reports SAEs (Serious Adverse Events) to Washington University IRB (Institutional Review Board), responsible for maintenance of REDCap electronic database, reporting to steering committee, ethics committee applications, data verification, recruitment, randomization, and follow-up of study participants

Data Management Committee:

[name], MSc
[name]

Responsibilities include: statistical design of study, data verification.

Data Adjudication Committee:

Responsibilities include: regularly reviewing delirium assessments, contacting trial management committee, retraining researchers if necessary.

Data and Safety Monitoring Committee:

[name], M.S., PhD - Yale University

[name] [name], FGSA, FAAN - Pennsylvania State University

[name], MD - Johns Hopkins University School of Medicine

[name] – Vanderbilt University Medical Center

[name] - Johns Hopkins Hospital

Safety Officer:

[name]- Johns Hopkins University School of Medicine

Responsibilities include: reviewing and evaluating the study data to ensure participant safety, study conduct, progress, and efficacy, and making recommendations regarding the continuation, modification, and termination of the trial.

INTRODUCTION: Postoperative delirium, arbitrarily defined as occurring within five days of surgery, affects up to 50% of patients older than sixty after a major operation. This geriatric syndrome is associated with longer intensive care unit and hospital stay, readmission, persistent cognitive deterioration, and mortality. No effective preventive methods have been identified, but preliminary evidence suggests that electroencephalography (EEG) monitoring during general anesthesia, by facilitating reduced anesthetic exposure and EEG suppression, might decrease incident postoperative delirium. This study hypothesizes that EEG-guidance of anesthetic administration prevents postoperative delirium and downstream sequelae, including falls and decreased quality of life.

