We will design a prospective matched cohort study using the ENGAGES participants (received multi-

All statistical analyses will be performed using SAS, version 9.4 (SAS Institute, Inc., Cary, North Carolina). All tests will be two-sided and by arbitrary convention¹⁰⁵ will be considered statistically significant at a $p<0.05$, and all results will be presented with estimates and 95% confidence intervals. However, based on the uncertain prior probability (plausibility) of the alternative hypothesis¹⁰⁶ (i.e., EEG guidance of anesthesia decreases postoperative delirium) and concerns raised about lack of reproducibility in science^{107,108}, a statistically significant result with a p value just <0.05 should be considered as preliminary, and future studies should be conducted for corroboration. A more stringent p value (e.g., $p<0.005$) would be required to conclude that subsequent studies would be very likely to reproduce these results with a p value <0.05 .¹⁰⁹ Apart from statistical significance, the ultimate decision regarding the routine implementation of EEG-guidance of general anesthesia in preventing postoperative delirium will also depend on the estimated effect size of this intervention.

Sample Size Calculations

All sample size calculations have been performed using SAS PROC POWER.

i) Decrease in Delirium

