The following limitations should be considered. A single clinical trial should seldom be regarded as definitive. As there is no clear estimate for the prior probability that EEG guidance of anesthesia prevents postoperative delirium, if the results of this trial do suggest that EEG-guidance of anesthesia might decrease delirium at the arbitrary statistical threshold of $p < 0.05$, it will be necessary to replicate this finding in future studies. On the other hand, even if the study finds a non-significant (at the arbitrary threshold of $p > 0.05$) decrease in delirium in the EEG-guided group, it is likely that follow-up studies will be warranted to clarify whether or not there is a clinically meaningful reduction in delirium with EEG-guidance of anesthesia, and whether there are specific patient populations that might especially benefit from this intervention. If EEG-guidance of anesthesia can prevent postoperative delirium, demonstrating its effectiveness will depend on clinicians' adherence to the protocol. However, the inability to blind clinicians to the trial allocation group is a potential source of bias and confounding. We are attempting to confirm that clinicians do alter anesthetic management based on the intervention during the pilot phase of the study. The inclusion of patients in a clinical trial focused on the prevention of delirium, and the provision of practical educational information to patients and family members could decrease the incidence of postoperative delirium. Furthermore, if the multi-component intervention is successful in preventing falls and in improving quality of life, this could curtail our ability to detect an impact of the EEG-guided anesthetic protocol on these outcomes. In addition to the pragmatic structured chart review, there are two clinical assessment methods that will be used to diagnose delirium: the CAM-ICU and the CAM. The CAM-ICU is less sensitive than the CAM, but is the only instrument that has been validated for patients who are non-verbal (i.e., with a breathing tube or tracheostomy in place). Based on our institutional data, the vast majority of patients enrolled in the study will be extubated within the first two postoperative days. Therefore, most patients will have delirium assessments with the CAM, which is the more sensitive and specific instrument. We will also test whether intubation status modifies the result in secondary analysis. The study design includes a 30-day and a 1-year follow up for patient reported outcomes, and incomplete follow-up is therefore a potential limitation. Based on our previous B-Unaware and BAG-RECALL studies,^{40,41} we are confident that we can achieve a 30-day follow up rate of >90%. In our SATISFY-SOS cohort, the 1-year follow up has yielded approximately 66% response rate. We have performed sensitivity analysis in our power calculations and have taken into account this potential attrition in our methods. Furthermore, we plan to enhance follow-up by using supplementary phone calls from members of the study team. As delirium is a fluctuating disorder, there is a risk that it can be missed by periodic assessments. We are attempting to mitigate this by assessing patients for delirium during a time of day (afternoon/evening) when delirium occurs more commonly. Furthermore, we are incorporating structured chart review, which has been validated as a complementary approach that increases the detection of delirium.^{93,94}

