Patients in the EEG-guided anesthetic group will, on average, receive decreased concentrations of inhaled anesthetic agents during their surgeries. Reduction of anesthetic administration using simultaneous EEG-based monitoring of anesthetic depth has been previously described without reports of increased intraoperative awareness.^{27,122} However, it is theoretically plausible that a significantly higher rate of awareness events could occur in a cohort that on average receives lower anesthetic concentrations. Therefore, we propose comparing the incidence of intraoperative awareness reports in the EEG-guided and usual care groups. We will recommend to the DSMB that this occur after 600 patients have been enrolled. A one-tailed comparison will be used to compare the incidences of awareness in the groups, and consideration should be given to terminating the study if the EEG-guided cohort has a significantly greater incidence of intraoperative awareness compared with the standard of care group with a p value <0.05. In making recommendations, the DSMB could take into consideration the severity of the awareness experiences, including reports of pain, paralysis and distress.¹²³ Apart from intraoperative awareness, it is not currently hypothesized that decreased anesthetic administration is associated with clinically relevant adverse outcomes (e.g. death, myocardial infarction, stroke). It is possible that decreases anesthetic administration might be associated with intraoperative patient movement, or with increased intraoperative blood pressure and heart rate. However, these are surrogate measures with unclear clinical relevance, which should not therefore impact a decision to terminate the study early.

We recommend to the DSMB not performing an interim analysis of delirium rates for any consideration of termination. Currently available data support the possibility that an EEG-guided anesthetic management to reduce anesthetic administration might decrease the incidence of postoperative delirium or have no effect on this outcome.²⁶⁻²⁹ Conversely, the possible finding of a higher incidence of delirium in the EEG-guided cohort would conflict with current evidence. When interpreted in the context of existing evidence, the finding of significantly disparate incidences of postoperative delirium in a partially completed ENGAGES trial would not provide a sufficient evidence base to change the standard of practice for anesthetic guidance of these patients.

Indemnity

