Delirium incidence, duration and severity have all been shown to be associated with other (downstream) clinically relevant outcomes, including mortality, length of ICU stay, length of hospital stay, falls, cognitive decline and functional decline. In the ENGAGES study, these associations will be explored. The data on downstream outcomes will be obtained from hospital records or from patient reported outcomes measures that are collected as part of the ongoing SATISFY-SOS study.

e) Comparison of patient-reported and observational pain scores

It is likely that patients with delirium are less able to convey verbally the extent to which they are in pain.¹³⁰ Given that postoperative delirium is common and may relate to uncontrolled pain, this has important implications for the assessment and treatment of postoperative pain. We plan to compare patient reported and behavioral pain assessments in both non-delirious and delirious patients.¹³⁰ (See Appendices for pain assessment instruments)

(conducted with the CAM-ICU) will be collected when these are available. Comparison will be made between these routine clinical assessments and the assessments made by the research team.

h) Association Between Delirium and Patient Outcomes

The ENGAGES study will evaluate the association between postoperative delirium and patient reported outcome metrics, including quality of life and falls, up to one year postoperatively.

i) Postoperative outcomes hypothesized to be associated with anesthetic depth

It is likely that patients randomized to the EEG-guided protocol will be exposed to lower concentrations of anesthetic agents, and on average will not be as deeply anesthetized. There is an ongoing randomized, clinical trial investigating the effects of depth of anesthesia on a range of outcomes^{101,102}, including death, myocardial infarction, cardiac arrest, pulmonary embolus, stroke, surgical site infection, ICU length of stay, hospital length of stay, intraoperative awareness, persistent pain and cancer recurrence. Many of these outcomes are tracked with the SATISFY-SOS study, and will therefore be reported for patients enrolled in the ENGAGES study.

j) Delirium Prediction Models

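### The advice to the DSMB against any interim look at delirium rules out harm as well as benefit, and does not fit the protocol's own safety provisions

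*Combined protocol and SAP*

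**What the plan says.** All references are to the combined protocol and SAP.

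- **Premature Study Termination, delirium.** "We recommend to the DSMB not performing an interim analysis of delirium rates for any consideration of termination". No exception is made for harm. Two reasons follow. First, available data suggest that EEG guidance "might decrease the incidence of postoperative delirium or have no effect on this outcome", whereas "the possible finding of a higher incidence of delirium in the EEG-guided cohort would conflict with current evidence". Second, a significant disparity in a partly completed trial would not be enough evidence to change anesthetic practice.
- **Premature Study Termination, awareness.** The section notes that earlier studies of reduced anesthetic administration did not report more awareness. It calls an increase theoretically plausible all the same, and proposes a one-tailed by-arm comparison at p<0.05 after 600 patients.
- **Adverse Event Reporting and Safety Monitoring.** The DSMB meets twice a year on safety events. Early stopping is allowed for safety, but not for efficacy or futility. The DSMB is advisory.
- **Organizational Structure and Responsibilities.** The monitoring committee's duties are "reviewing and evaluating the study data to ensure participant safety, study conduct, progress, and efficacy", together with recommendations on continuing, modifying or terminating the trial.
- **Addendum, sub-study d.** Delirium is described as associated with mortality and with cognitive and functional decline.

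**The concern.** A bar on efficacy and futility stopping is a defensible design choice, and the protocol argues for it. The delirium recommendation goes further, because its wording also removes a higher delirium rate in the EEG arm from any decision about termination. On the protocol's own account delirium is a serious event, so an excess of it would be a safety matter. The DSMB is then left with texts that point in different directions: review safety and efficacy data and advise on termination, stop for safety if needed, but do not analyze the primary outcome for that purpose.

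If EEG guidance did increase delirium, the patients exposed would be those enrolled after the point at which the committee could have seen it. After the planned 600-patient look, 1,232 − 600 = 632 patients remain, about 316 of them in the EEG arm. At the anticipated 300 to 400 patients per year they would take about 632/400 = 1.6 to 632/300 = 2.1 years to enroll, which spans three or four scheduled DSMB meetings.

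**Working it through.** **1. The stated reasons, set against the rest of the text.**

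- *Conflict with current evidence.* The meta-analysis in the Background gives a pooled odds ratio of 0.56 (0.42 to 0.73). At 25% control delirium the odds are 0.25/0.75 = 0.333; times 0.56 this is 0.187, or 0.187/1.187 = 15.7% (12.3% to 19.6% over the interval). An increase would indeed run against that evidence. For awareness, however, the same section treats reassuring earlier data as no bar to a planned look. The two outcomes are held to different standards.
- *Not enough to change practice.* Whether an interim result should alter practice elsewhere is a different question from whether more patients should be randomized to an arm that is doing worse.

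**2. The plan's own power figures.** With 616 per arm, 25% control delirium, two-sided 5% and a pooled-null z test, power for decreases of 7, 8 and 9 points is 84.9%, 93.2% and 97.5%. The stated lower bounds (80%, 90%, 95%) are met. For increases of the same size, final power is 77.7%, 87.3% and 93.5%, so the design can detect harm at the end.

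**3. What one harm-only look could detect.** Inputs: 300 per arm (600 patients, 1:1), 25% control delirium from the sample size section, and one-sided 0.001 (z = 3.090), assumed for illustration only.

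Power = Φ(d/SE − 3.090), with SE = √[p₀(1−p₀)/300 + p₁(1−p₁)/300].

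| EEG arm | d | SE | d/SE − 3.090 | Power |
|---|---|---|---|---|
| 30% | 0.05 | 0.0364 | −1.717 | 4% |
| 35% | 0.10 | 0.0372 | −0.402 | 34% |
| 40% | 0.15 | 0.0377 | 0.883 | 81% |

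A looser level detects more. For a 10-point excess, power is about 54% at 0.005 and 76% at 0.025.

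**4. Cases at stake.** Expected EEG-arm cases averted = 316 × excess × power, if enrollment stopped at once:

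- 5 points: 15.8 × 0.043 = 0.7, about 1
- 10 points: 31.6 × 0.34 = about 11
- 15 points: 47.4 × 0.81 = about 38

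**5. False alarms.**

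- One look at 0.001 with no true effect: 0.1%.
- One look under the planned benefit (18% against 25%): SE = 0.0334, and Φ(−0.07/0.0334 − 3.090) = Φ(−5.18), about 1 in 10 million.
- Eight equally spaced looks (assumed from roughly four years of twice-yearly meetings, the last at full enrollment), by simulation with no true effect: about 0.5% at 0.001, 2% at 0.005 and 9% at 0.025.

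**6. Effect on the test for benefit.** A harm-only stop can only remove trials from the set that would later claim benefit, so it cannot raise that error. In 2 million simulated trials, with a look at 300 per arm and the final test at 616, the error for benefit was 0.025 with and without the look. Power at 18% against 25% was 85.1% both ways.

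**The case against.** The strongest reply is that this is a recommendation to an independent board, not an instruction. The board keeps a general power to advise stopping for safety and a wide remit to evaluate data. Both facts are true and they soften the point. They do not remove it, because the specific wording on delirium excludes any termination purpose and would be read as qualifying the general provision. Text just before the DSMB paragraph is missing from the copy available, so a further safety provision there cannot be excluded; it too would have to be squared with the explicit delirium wording.

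Two stronger readings are tempting, and the documents support neither.

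- *That the protocol contradicts itself on the prior.* It says "there is no clear estimate for the prior probability that EEG guidance of anesthesia prevents postoperative delirium" and, on significance levels, "based on the uncertain prior probability (plausibility) of the alternative hypothesis". Both statements concern whether the benefit is real. Expecting a decrease or no effect is compatible with that, and agrees with the pooled odds ratio. Two-sided testing is adopted as a general convention and asserts nothing about how likely harm is.
- *That the protocol contradicts itself on death, infarction and stroke.* The termination section says "it is not currently hypothesized that decreased anesthetic administration is associated with clinically relevant adverse outcomes (e.g. death, myocardial infarction, stroke", while sub-study i is headed "Postoperative outcomes hypothesized to be associated with anesthetic depth". The first concerns harm from less anesthetic. The second concerns depth, and in this protocol the suspected harm lies with deep anesthesia. The two are compatible.

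It is also fair to object that 32 to 47 excess cases (10 to 15 points among 316 patients) overstates what a look would prevent. Those are cases at stake. The expected number averted is lower once the chance of detection is applied. Repeated looks also cost more in false alarms than a single one.

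**Conclusion.** The recommendation excludes harm monitoring on the primary outcome. Neither stated reason supports that exclusion. It is in tension with the awareness look in the same section, and it does not fit the safety-stopping provision, the committee's remit or the protocol's account of delirium's consequences. This should be changed.

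The size is moderate and conditional. With a 25% control rate, 300 per arm and one look at one-sided 0.001, a 5-point excess would almost always be missed (4%), a 10-point excess found about one time in three, and a 15-point excess about four times in five. Expected cases averted are about 1, 11 and 38 if enrollment stopped immediately. The harm sizes and the threshold are assumptions. Protecting type I error for benefit is not a reason to omit the look. The false-alarm risk is small for one strict look, but reaches about 9% for eight looks at 0.025, so it depends on the rule chosen.

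**What to change.** 1. In Premature Study Termination, limit the recommendation against interim delirium analysis to efficacy and futility. Suggested wording: *Delirium rates will not be analyzed at interim for stopping for efficacy or futility. At the 600-patient review the DSMB will receive delirium incidence and deaths by arm, with confidence intervals, in closed session, for the assessment of harm only.*
2. Have the DSMB set its harm guideline, and the number and timing of any further looks, in its charter before the first look, so that the overall false-alarm probability is controlled. The 0.001 level above is an illustration, not a proposed rule.
3. Reconcile the committee's duties under Organizational Structure and Responsibilities, the stopping provisions under Adverse Event Reporting and Safety Monitoring, and Premature Study Termination, so that all three give the DSMB the same remit.

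The cost is protocol and charter wording plus one closed-session table. Incident delirium is assessed to postoperative day 5, so the data should be nearly complete at the look. No extra patients are needed and no alpha is spent on benefit. The downside is a small chance of a false harm signal, which depends on the guideline and the number of looks.
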